PROTOCOL TITLE: Self-Catheterization Mirror System for Female Patients

PRINCIPAL INVESTIGATOR:

[name] Shirley Ryan AbilityLab [contact] [contact]

VERSION DATE:

11.22.2021

STUDY SUMMARY:

Investigational Agent(s) (Drugs or Devices)	Self-Catheterization Mirror
IND / IDE / HDE #	
Indicate Special Population(s)	None
Sample Size	30
Funding Source	Shirley Ryan AbilityLab
Indicate the type of consent to be obtained	Written
Site	Shirley Ryan Ability Lab
Research Related Radiation Exposure	No
DSMB / DMC / IDMC	No

Version Date: 11.22.2021 Page 1 of 10 HRP-593 / v05202020

OBJECTIVES:

The purpose of this study is to evaluate the usability of a modified self-catheterization mirror compared to a standard self-catheterization mirror as well as to obtain user feedback through patient experience with the use of a modified self-catheterization mirror.

BACKGROUND:

Intermittent catheterization is a procedure to empty the bladder for individuals with voiding difficulties, such as resulting from neurologic injury (e.g., spinal cord injury or multiple sclerosis) or obstruction. IC can maintain or improve urological function and to reduce the risk of bladder infections [1,2]. Self-catheterization is a standard method for managing short-term or long-term bladder dysfunction for many individuals. However, many female patients have difficulties with self-catheterization [3]. Mirrors currently used for this procedure have insufficient stability and visibility to easily view the urethral opening during catheterization, particularly for individuals with motor impairments and urinary retention related to spinal cord injury or other medical conditions. This can be especially frustrating because catheterization is performed frequently (typically every 4-6 hours) and may need to occur at home or in public facilities.

Figure 1. The standard self-catheterization mirror for female patients. This setup poses significant challenges for female patients to catheterize themselves, with limited stability and visibility to view the urethral opening.

This project will develop and test a portable, cost-effective product to help female patients with a range of motor abilities catheterize themselves in various postures and settings. The long-term goal is to improve the self-catheterization experience for patients during inpatient education and after hospital discharge.

STUDY ENDPOINTS:

Our primary outcome is the patient-reported usability and experience when using the mirror. Our secondary outcome is the average time needed to set up the mirror and self-catheterize. These measures will be obtained for all patients and compared between the modified mirror and the standard mirror.

We expect that participants will be in this research study during two weeks of their inpatient rehabilitation stay at the Shirley Ryan AbilityLab, spanning two phases of testing that will each last up to 1 week.

Version Date: 11.22.2021 Page 2 of 10 HRP-593 / v05202020

STUDY INTERVENTION(S) / INVESTIGATIONAL AGENT(S):

We have developed modifications to a standard catheter mirror, which are intended to improve stability and visibility during the self-catheterization procedure for women with motor impairments and urinary retention related to spinal cord injury or other medical conditions. The modified mirror (**Figure 2**) features the standard catheter mirror, held in a surrounding case, with adjustable straps for suspension between the legs whether the individual is in a seated position, reclined, or in a standing position. This also provides flexibility for the mirror's angle to be manipulated for better viewing. The mirror also features LED lights that can be turned on to improve visibility, so that individuals may view the urethral opening easier during catheterization.

Figure 2. The modified self-catheterization mirror system includes the standard mirror, held in a surrounding case, with adjustable straps for suspension between the legs and LED lights that can be turned on/off.

All modified self-catheterization mirrors will be stored in a locked area at Shirley Ryan AbilityLab and will only be accessible to immediate study team members.

PROCEDURES INVOLVED:

Screening: This study will involve recruitment of female patients participating in self-catheterization at the Shirley Ryan AbilityLab (SRAlab). Clinicians at this location will be informed of the inclusion and exclusion criteria for this study in order to refer appropriate patients to the study. Potential research subjects will be referred to authorized research personnel and will also be identified based on inclusion and exclusion criteria using the Cerner application.

Testing: There will be two phases of the testing, with each phase lasting up to 1 week. **Phase 1** will test their experience with the standard mirror, and **Phase 2** will test their experience with the modified mirror. This order is determined so that all participants attain practice with self-catheterization and study procedures with the standard mirror first, in alignment with the standard of care. The modified mirror will not be given to the participants until Phase 2 testing begins.

Phase 1 (Standard mirror): Subjects will self-catheterize every 4-6 hours, depending on their physician's orders, using the standard mirror. This will allow the subjects to self-catheterize at different times of the day and in various positions. This mirror will have already been provided for self-catheterizing patients by the hospital, and patients will have been trained to self-catheterize by their standard care team.

Version Date: 11.22.2021 Page 3 of 10 HRP-593 / v05202020 Subjects will be given a log sheet specifying the catheterization trial number and the assigned mirror. For each catheterization, subjects will record the position used, the mirror used, and the time it took to complete mirror set up and successfully insert a catheter. They will record this information after each catheterization within the phase.

Phase 2 (Modified mirror): Upon completion of Phase 1 testing, subjects will be trained to use the features of the modified mirror in a single training session. Study staff will demonstrate the attachment of the mirror and help the subject practice the attachment and use of the mirror in any of the positions (seated, reclined in the patient's hospital bed, and standing). If a subject is unable to achieve and maintain a position independently or with minimal assistance, the training in that position will be skipped. Study staff will confirm any positions that the subject uses to self-catheterize (confirmed against the Phase 1 log sheet), and train the subject to utilize the modified mirror in those positions. Training will be considered successful if the subject can set up the modified mirror 3 times independently in all possible self-catheterization positions. At the end of the training session, the subject will be asked if they would be comfortable using the mirror independently.

A subsequent training session will be scheduled if the subject (1) cannot set up the modified mirror 3 times independently in their possible self-catheterization positions, or (2) does not feel comfortable using the mirror independently. If the subject does not meet these criteria after a second training session, they will be asked to fill out a questionnaire regarding their experience with the device (see "Questionnaires" below) and study procedures will end; patients who do not complete a successful training session will not be invited to complete Phase 2 testing.

Immediately following the completion of a successful training session, subjects will begin the Phase 2 testing, following identical procedures as in Phase 1 but asked to use the modified mirror. Subjects will record the mirror used, position, and time for self-catheterization in a new log sheet. Subjects will continue to have the standard mirror during this phase, and will be encouraged to use this standard mirror instead for any trial if needed for successful self-catheterization.

Questionnaires: Subjects will complete a questionnaire (System Usability Scale) at the end of each testing phase related to self-operation and user satisfaction with the use of the assigned mirror. They may also complete these questionnaires at the completion of the study.

DATA AND SPECIMEN BANKING

Data will be collected and kept confidential and compliant with HIPAA requirements. All personal information and study documentation that can identify participants will be kept secure to protect their privacy and will never be shared at any time with any person or entity. Data collected during the study and shared with others will reference participants only by an alphanumeric code (i.e., de-identified). The "master list" linking personal information to the alphanumeric code will not be shared. Electronic data will be stored on a secure and password-protected network and devices managed by the Shirley Ryan AbilityLab. Electronic folders will be private with limited access as determined by the PI.

Version Date: 11.22.2021 Page 4 of 10 HRP-593 / v05202020 De-identified data will be stored indefinitely. If participants give written consent to be contacted for future studies, this information will be kept separate from de-identified data files, in locked cabinets accessible only by authorized research personnel. All other information will be destroyed in accordance with HIPAA and IRB compliant guidelines.

SHARING RESULTS WITH PARTICIPANTS

Participants will be recording their own results in a time log, as well as providing their own experiences and satisfaction with the use of a modified mirror during self-catheterization. There is no intent to share additional information about results with participants.

STUDY TIMELINES

- Subjects will each participate in the study for two testing phases, each lasting a period of up to 1 week
- This study will enroll participants for up to 9 months.
- This study is projected to be completed by June 2023

INCLUSION AND EXCLUSION CRITERIA

Inclusion Criteria:

- Females age 13 or older
- Urinary retention related to spinal cord injury or other medical conditions resulting in need for catheterization
- Individuals with sufficient upper limb function to catheterize independently or with minimal assistance, or as deemed appropriate for the study by the Principle Investigator.

Exclusion Criteria:

- Individuals younger than 13 years old
- Individuals with cognitive deficits or visual impairments that may impact safe use of the devices used
- Severe ROM restrictions of the upper and/or lower extremities
- Pregnant

RECRUITMENT METHODS

This study will involve recruitment of individuals who require self-catheterization due to urinary retention related to spinal cord injury or other medical conditions. Clinicians at Shirley Ryan AbilityLab (18th-25th floors) will be informed of the inclusion and exclusion criteria for this study for the referral of appropriate subjects. Potential subjects will be screened and evaluated by the research team. Clinicians on the 18th-25th floors will be trained on the use of the modified mirror and will help introduce the modified mirror to eligible and willing participants.

COMPENSATION FOR PARTICIPATION IN RESEARCH ACTIVITIES

Participants will be compensated up to \$20 for their participation through the ClinCard system. When a subject completes participation, funds will be approved and loaded onto the card. These funds are provided for the subject's participation in the study.

Version Date: 11.22.2021 Page 5 of 10 HRP-593 / v05202020 For each participant, SRAlab will issue a ClinCard, which is a specially designed debit card for clinical research. Funds will be loaded as appropriate. The funds will be available within 1 day after being loaded and can be used at the participant's discretion. Participants will be issued one card for the duration of the study. If the participant withdraws from the study early, she will be reimbursed for these expenses for the portion of the study that was completed. If the card is lost or stolen, participants may call [contact] or ask a coordinator for a replacement ClinCard.

WITHDRAWAL OF PARTICIPANTS

If a participant has an adverse event, requiring therapeutic intervention and/or the experience interrupts usual daily activities, the subject will be withdrawn from the research study without their consent. This may include injury or impaired skin integrity due to the use of the modified mirror.

If a participant chooses to withdraw from the study, they will be thanked for their time and asked if they wish to disclose why they have decided to withdraw from the study. From that point, all data that was already collected on the participant will be retained and missing data from continued data collection will be treated as a loss to follow up.

RISKS TO PARTICIPANTS

The modified self-catheterization mirror is a prototype device with no significant risk to participants. The device utilizes a standard catheter mirror, enables it to be suspended between the legs, and improves visibility using commercially-available resources such as adjustable straps and miniaturized LED lights. The system can easily be adjusted to fit participants and adhere to different positional needs during self-catheterization. Use of the device can be stopped at any time when completing self-catheterization.

Physical risks from this study may include skin breakdown, urinary tract infection, and muscle soreness.

- Another possible risk is discomfort, skin pressure/friction, or bruising caused by the
 device straps, which has the potential to lead to skin breakdown or abrasions. This risk
 will be minimized by a thorough skin check performed by clinicians before and after
 device use, and application of foam dressings or bandages as needed. Use of the
 modified mirror will be discontinued for any participant with skin breakdown.
- Risk of a urinary tract infection due to use of the device. This risk will be minimized by emphasis of utilizing a sterile environment during self-catheterization and following hospital protocols regarding hygiene and cleanliness of devices and equipment.
- There is a risk of muscle soreness from being in a certain position for a prolonged period
 of time during the self-catheterization process. Clinicians will monitor subject activity and
 subjective reports of pain or discomfort throughout the process. Assisted repositioning
 and/or rest periods will be provided as needed.
- Embarrassment or discomfort discussing self-care may be associated with this study. All staff members assisting with this study are trained professionals and familiar with the intermittent catheterization process.

Version Date: 11.22.2021 Page 6 of 10 HRP-593 / v05202020 Clinicians will monitor device functionality and participant comfort during use and intervene if an unforeseen challenge occurs. During study procedures, a standard mirror will always be available to the patient if needed in the event that use of the modified mirror is obstructive to the self-catheterization process.

Risk of confidentiality will be minimized by not including personal identifying information on forms (Self-Catherization Log, questionnaire, etc.) and by conducting data collection in a private setting.

Some of the questions included in the questionnaire may be upsetting or uncomfortable for the participant to answer. If they do not wish to answer a question, they may skip it.

No psychological, financial, or legal risks to participants are anticipated.

POTENTIAL BENEFITS TO PARTICIPANTS

There may be no direct benefit to the participants. The main benefit of participation in this study is understanding the real-world challenges faced by patients performing self-catheterization, which may help other people through future development of devices and procedures. The modified mirror is intended to increase stability and visibility for individuals needing to self-catheterize, and ultimately, make the self-catheterization process easier for them. There is potential for participants to experience these benefits during use.

DATA MANAGEMENT AND CONFIDENTIALITY

Data will be collected and kept confidential and compliant with HIPAA requirements. All personal information and study documentation that can identify participants will be kept secure to protect their privacy and will never be shared at any time with any person or entity. Data collected during the study and shared with others will reference participants only by alphanumeric code. The "master list" linking personal information to the alphanumeric code will not be shared. Electronic data will be stored on a secure and password protected network and devices managed by the Shirley Ryan AbilityLab. Electronic folders will be private with limited access as determined by the PI.

PROVISIONS TO MONITOR THE DATA TO ENSURE THE SAFETY OF PARTICIPANTS

Data will be reviewed by researchers after each intervention session. Any and all adverse events will be documented and reported in compliance with IRB regulations. If they occur in the presence of researchers, prompt medical attention will be requested via assessment by the resident on call. Health status will be assessed at all visits to ensure participant safety. Events will be recorded in case report forms. Participants will be encouraged to contact research staff or the PI to report any changes in health status. If participants experience major changes in health status, study participation will either be suspended or terminated depending on severity.

If any new information is identified concerning the safety of the study device, participants will be notified. This available information may affect the participant's decision to remain in the study.

PROVISIONS TO PROTECT THE PRIVACY INTERESTS OF PARTICIPANTS

Version Date: 11.22.2021 Page 7 of 10 HRP-593 / v05202020 Subject records will be kept confidential. Precautions will be taken to protect the privacy interests of subjects. Participation in this study is completely voluntary. The purpose of the study and intended use of a subject's medical information as well as precautions taken to keep the study information and data confidential will all be explained to each participant. All collected data will be kept confidential and compliant with HIPAA standards.

COMPENSATION FOR RESEARCH-RELATED INJURY

The PI of the study is required to be notified promptly in the instance of any injury or illness inflicted on the participant as a result of the study. The hospital [Researchers, Shirley Ryan AbilityLab, Northwestern University and all affiliated clinical sites] will not pay for medical care required because of a bad outcome resulting from participation in this study. However, the subject may still seek to get paid back for care required because of a bad outcome resulting from participation in this study.

ECONOMIC BURDEN TO PARTICIPANTS

Subjects will be compensated for their participation in the study.

CONSENT PROCESS

Before recruitment and enrollment onto this study, the participant will be given a full explanation of the study and will be given the opportunity to review the consent form. Each consent form must include all the relevant elements as approved by the Northwestern University Institutional Review Board.

Trained research personnel will guide the participant through consenting process. Participant will be given detailed explanation of the purpose, time line, commitment, procedures, data handling, and privacy and confidentiality of information pertaining to the study. Once this essential information has been provided to the participant and the investigator is assured that the participant understands the implications of participating in the study, the participant will be asked to give consent to participate in the study by signing an IRB approved consent form. Subjects will be consented with a new consent form if changes are made to the protocol. Prior to participation in the trial, the written informed consent form must be signed and personally dated by the participant or authorized guardian and by the person who conducted the informed consent discussion.

The consent process will take place at the Shirley Ryan AbilityLab in Room 11-1401 or on an AbilityLab floor (patient room or private meeting space).

PARTICIPANTS WHO ARE NOT YET ADULTS (infants, children, teenagers)

Participants will be asked their age upon study screen. Any child under the age of 18 years will be considered a minor. If the participant is determined a minor, every effort will be made to ensure the screening process proceeds with a parent or an authorized legal guardian present. The consent and protocol will be explained by a trained researcher to both the present parent/authorized legal guardian and the minor. The parent or authorized legal guardian will then be asked to consent on behalf of the minor, in accordance with the DHHS and the USFDA's subpart D. The parent or authorized legal guardian will also be given the opportunity present at all training and testing sessions.

Version Date: 11.22.2021 Page 8 of 10 HRP-593 / v05202020 Consent will be obtained from one parent even if the other parent is alive, known, competent, reasonably available, and shares legal responsibility for the care and custody of the child. This will be done to ensure the protocol is carried through in a timely manner.

Permission will also be obtained from an authorized legal guardian if necessary. Efforts will be made to determine whether the guardian is in fact legally authorized by ensuring the child lives with the aforementioned guardian. Assent will be obtained from all children. Verbal assent will be obtained for children unable to give written consent. Assent will be documented in the IRB approved consent form.

NON-ENGLISH SPEAKING PARTICIPANTS

Non-English speaking subjects will be permissible for recruitment and enrollment in the study (Spanish, Arabic, and Polish).

An interpreter who speaks the participant's primary language will be scheduled through the Shirley Ryan AbilityLab Interpreter Services department to attend all research appointments during which the participant is scheduled if necessary as determined by the participant.

PROTECTED HEALTH INFORMATION (PHI AND HIPAA)

Subjects records will be kept completely confidential. Every possible precaution will be taken to protect the privacy interests of subjects. Trained research personnel will explain the purpose of the study and intended use of a subject's medical information and the precautions taken to keep the study information and data confidential. Data will be collected and kept confidential and compliant with HIPAA standards.

Participants will be assigned an alphanumeric study ID. Identifying data will be kept in locked cabinets and password protected servers completely separate from de-identified data. Research data will be de-identified and stored in locked cabinets in the lab accessible only by authorized research personnel. Electronic data will be de-identified and kept on secure, password protected servers at the Shirley Ryan Ability Lab. Only authorized research staff will be able to access any of the formerly mentioned data. De-identified data will be kept indefinitely.

Study documentation will be collected and stored and kept confidential and compliant with HIPAA requirements. Identifying data will be held for 7 years after the study is completed and published.

All personal information (names, addresses, email or phone numbers, etc.) gathered for this study that can identify participants will be kept secure to protect their privacy and will never be shared at any time with any person or entity. Data collected during the study and shared with others will reference participants only by an alphanumeric code. The "master list" linking personal information to the alphanumeric code will not be shared, and will be kept by the study PI in a secure location. All personal information linking participants to their data will be destroyed after 7 years following the completion of the study

QUALIFICATIONS TO CONDUCT RESEARCH AND RESOURCES AVAILABLE

All sessions will occur at Shirley Ryan AbilityLab ([name])

Version Date: 11.22.2021 Page 9 of 10 HRP-593 / v05202020 An acute inpatient rehabilitation and research hospital. Each unit is staffed with 21 full time employee nurses; with virtually no cross-over. Study procedures will occur on the inpatient floor in private, single-patient care rooms.

All study team members will be trained on the study protocol and procedures. The study team members are employees of the Shirley Ryan AbilityLab. They are familiar with the study site and are experienced with the study population. There will be medical resources including a resident on call and nursing staff available 24 hours a day if needed in case of an emergency.

REFERENCES

- 1. Wyndaele, J. Intermittent catheterization: which is the optimal technique? *Spinal Cord* **40**, 432–437 (2002). https://doi.org/10.1038/sj.sc.3101312

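### Logged time is defined only up to successful insertion and no listed log field records success or failure, so the secondary time comparison is conditional on success

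*Protocol*

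**What the plan says.** Study Endpoints sets the time outcome: "Our secondary outcome is the average time needed to set up the mirror and self-catheterize". It adds: "These measures will be obtained for all patients and compared between the modified mirror and the standard mirror".

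Procedures Involved gives the only working definition of that time. In Phase 1 the log sheet carries the trial number and the assigned mirror. The instruction is then: "For each catheterization, subjects will record the position used, the mirror used". A duration completes the list of items, and the protocol words it as "the time it took to complete mirror set up and successfully insert a catheter". On timing it says: "They will record this information after each catheterization within the phase".

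Phase 2 follows identical procedures: "Subjects will record the mirror used, position, and time for self-catheterization in a new log sheet". The standard mirror stays with the subject, who is "encouraged to use this standard mirror instead for any trial if needed for successful self-catheterization". Phase 1 has no counterpart to this fallback, because the modified mirror is withheld until Phase 2.

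The fields named across the two phases are therefore trial number, assigned mirror, position, mirror used and time. None is an outcome of the attempt.

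**The concern.** The time runs to a successful insertion. If an attempt ends without one, no value fits the definition, and the protocol does not say what to write instead. The protocol expects some such attempts in Phase 2, since it provides for a switch when the modified mirror does not lead to success.

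The two conditions also differ in what happens next. A failed standard-mirror attempt in Phase 1 has no second mirror and no defined time. A failed modified-mirror attempt in Phase 2 can end as a timed standard-mirror success, and the time spent before the switch has no place on the sheet.

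What is at stake is the direction and size of the secondary comparison. If one mirror turns would-be failures into slow successes, those slow trials enter its average, while the other mirror's average leaves the matching trials out. An analysis plan written later could not repair this, because outcomes and stopping times that were never collected cannot be recovered.

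**Working it through.** The protocol gives no failure rate, no time and no variance, so there is no figure to reproduce. The question is whether an average over successful trials can mislead, and under what conditions. All inputs below are assumptions.

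**Rows at issue.** With catheterization every 4 to 6 hours and a full 7-day phase, each woman contributes 7 × 24 / 6 = 28 to 7 × 24 / 4 = 42 trials per phase.

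**Model 1: failed trials have no time.** A share h of trials is hard. With the standard mirror an easy trial takes 4 min and a hard one 10 min. The modified mirror is d minutes faster on every trial. A hard trial succeeds with probability s, so the overall failure rate is h(1 − s). The logged mean is

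[(1 − h)(4 − d) + h·s·(10 − d)] / [(1 − h) + h·s], with d = 0 for the standard mirror.

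Worked case with h = 0.2, d = 0.25, s = 0.5 (standard) and 0.9 (modified):
- standard: (0.8 × 4 + 0.1 × 10) / 0.90 = 4.20 / 0.90 = 4.67 min
- modified: (0.8 × 3.75 + 0.18 × 9.75) / 0.98 = 4.755 / 0.98 = 4.85 min
- logged difference, modified minus standard: +0.19 min, against a true −0.25 min

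Further cases from the same formula:

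| h | True difference (min) | Failure, standard vs modified | Logged difference (min) | Effect |
|---|---|---|---|---|
| 0.1 | −0.50 | 5% vs 1% | −0.27 | diluted |
| 0.2 | −0.25 | 10% vs 2% | +0.19 | reversed |
| 0.3 | −0.50 | 15% vs 3% | +0.11 | reversed |
| 0.3 | −1.00 | 22.5% vs 3% | +0.09 | reversed |
| 0.2 | −0.25 | 10% vs 10% | −0.25 | no bias |
| 0.2 | −0.25 | 2% vs 10% | −0.69 | exaggerated |

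With a true gain of 1.0 min, the 22.5% vs 3% case was the only reversal among the values tried.

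**Model 2: Phase 2 switches.** Suppose the modified mirror is no faster, h = 0.2, and half of the hard Phase 2 trials are switched after 6 lost minutes.
- Phase 1 mean: 0.8 × 4 + 0.2 × 10 = 5.20 min
- Phase 2 trials completed with the modified mirror: (0.8 × 4 + 0.1 × 10) / 0.9 = 4.67 min, difference −0.53 min
- all Phase 2 trials with lost time counted: 0.8 × 4 + 0.1 × 10 + 0.1 × 16 = 5.80 min, difference +0.60 min

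Here the error favours the modified mirror.

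**Does averaging in the stopping times cure it?** Take 100 trials per mirror. Standard: 80 successes at 5 min and 20 failures stopped at a minutes. Modified: 80 successes at 5 min, 15 at 8 min and 5 failures stopped at a minutes. Successes only give 400/80 = 5.00 and 520/95 = 5.47 min. With stopping times averaged in, the means are 4 + 0.2a and 5.2 + 0.05a. The modified mirror is ahead only if 0.15a > 1.2, that is a > 8. At a = 10 the means are 6.00 and 5.70; at a = 6 they are 5.20 and 5.50. Success is 80% against 95% throughout. The ordering thus depends on how soon women give up, because a stopping time is only a lower bound on the time to success.

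**The case against.** A reader might infer that only successful catheterizations are logged and that failed ones vanish. The text does not say so. It asks for a record of each catheterization and excludes none; it is silent on what to enter after a failure. An abandoned trial could appear as a numbered row without a time. In Phase 2 a mismatch between assigned and used mirror shows that a switch took place. Repeated tries that end in success stay inside the logged time. The log form itself is a separate document and is not shown, so it may hold more than the protocol lists.

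The expected failure rate may also be low. The Background says "many female patients have difficulties with self-catheterization", but it describes poor stability and visibility, not a rate of failure. Participants have been trained by their care team, and Phase 2 starts only after successful training with the modified mirror.

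Finally, every reversal above rests on chosen inputs, and only a secondary outcome is touched.

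These points stand, and they limit the claim. They do not close the gap. A blank time cannot be told apart from a forgotten entry, a mirror mismatch gives neither the reason nor the time lost, and neither trace yields a success proportion.

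**Conclusion.** The point holds as a gap in data collection. The time is defined only up to success, no listed field records whether an attempt succeeded with the mirror tried, and the protocol foresees attempts that do not. The secondary comparison is therefore conditional on success.

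Its size is unknown, because the protocol gives no failure rates. Under the assumed values the bias ranges from none (equal rates) through dilution (−0.50 shown as −0.27 min at 5% vs 1%) to reversal (−0.25 shown as +0.19 min at 10% vs 2%), and it can run in either direction. Reversal in the first model needs failure rates that differ between mirrors by an amount that is large relative to the true gain. The stronger reading, that the comparison will point the wrong way, is not supported.

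The primary usability questionnaire is not directly affected. The change is still worth making, because it is cheap and the data cannot be recovered afterwards.

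**What to change.** Add to both log sheets, once for each mirror tried in a trial, a yes/no item, *catheter inserted with this mirror*, and the elapsed time at success or at stopping. If the form already has such an item, state it in Procedures Involved. This concerns recording only and leaves the rules on switching or stopping as they are.

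In Study Endpoints, state that the proportion of attempts successful will be reported by mirror beside the average time. In the time comparison, treat a failed attempt as censored at its stopping time, for example with a time-to-success summary. Because women probably stop when a trial is going badly, add a sensitivity analysis that ranks failures as worst. Neither averaging successes alone nor averaging stopping times as if they were completion times is adequate.

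The cost is a small added recording burden per trial, over up to 28 to 42 trials per woman in a full-week phase, and a few sentences in the protocol. The protocol does not say whether the log is already in use. If it is, rows recorded before the change will lack the item and should be identified as such.
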